### **Time to Alleviation of Influenza Signs and Symptoms**

Time to alleviation of influenza signs and symptoms (TTAS) in hours, will be summarized using descriptive statistics, as well as Kaplan-Meier plots. It is defined as the length of time taken from the start of treatment to the point at which all of the following criteria are met and remain so for at least 21.5 hours:

- A score of 0 (no problem) or 1 (minor problem) for cough and nasal symptoms (items 14 and 15 of the CARIFS questionnaire, see [Appendix 4](#)).
- A “yes” response to the following question on the CARIFS: “Since the last assessment has the subject been able to return to day care/school, or resume his or her normal daily activity in the same way as performed prior to developing the flu?”
- Return to afebrile state (tympanic temperature  $\leq 37.2^{\circ}\text{C}$ ).

If a score of 4 (“Don’t Know/Not Applicable”) occurs at any assessment during the study for items 14 or 15, the assessment will not be included in the calculation of the alleviation of symptoms because the assessment was unobservable.

Patients with symptom scores  $\leq 1$  for both items 14 and 15, as well as tympanic temperature  $\leq 37.2^{\circ}\text{C}$  and a “yes” response to the question “Since the last assessment has the subject been able to return to day care/school, or resume his or her normal daily activity in the same way as performed prior to developing the flu?” simultaneously at baseline will be excluded from the analysis.

Patients who do not experience alleviation of symptoms prior to completion or withdrawal from study will be censored at the last observation time point.

Baseline is defined as the first CARIFS assessment on Day 1 after the start of treatment. Patients who do not have a CARIFS assessment on Day 1 after the start of treatment will have their baseline CARIFS assessment set to missing.

The number of patients with completed CARIFS as well as the number with missing CARIFS per assessment will be presented for the ITT and ITTi sets. Additionally, the number and percentage of those with “Don’t Know/ Not Applicable” per question per assessment will be presented for the ITT and ITTi sets.

In the main analysis of the TTAS, only complete assessments (i.e., assessments that have responses for items 14 and 15 of the CARIFS questionnaire, the normal daily activity question and temperature) that do not have scores of 4 for items 14 and 15 are considered in the calculation of the TTAS. A sensitivity analysis will be conducted that considers all assessments in the calculation of the TTAS, where a score of 4 for items 14 or 15 does not break the incidence of alleviation.

In addition, a sensitivity analysis will be conducted in which the following criterion will be removed from the calculation of the TTAS:

- A “yes” response to the following question on the CARIFS: “Since the last assessment has the subject been able to return to day care/school, or resume his or her normal daily activity in the same way as performed prior to developing the flu?”

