**Table 4 CARIFS Questionnaire Data Recording Time Periods**

Period	Time a
Morning	05.00–10.59
Noon	11.00–14.59
Evening	15.00–18.59
Bedtime	19.00–23.59

a data should not be recorded between 00.00 and 04.59.

In the case where the device was activated after Day 1, the actual day will be used as the assessment day rather than the device-labelled day. In the case where assessments should be recorded twice daily (morning and evening) but are recorded for more than two time periods, only the morning and evening assessments will be presented in summaries over time. In the case where assessments should be recorded once daily but are recorded for more than one time period, a conservative approach will be taken to select the data points to be included in the summaries over time.

In the case where the recorded time of an assessment is outside the period time window for that assessment, the end time of the period should be imputed as the assessment time.

In the case where the assessment time falls into the period between 00.00 and 04.59 (due to technical error) the assessment date will be imputed to the date prior to recorded assessment date and the assessment time will be imputed to the end time of the period time window.

The possible scores for the 18 symptoms specified in the CARIFS questionnaire (see [Appendix 4](#)) are:

- 0 (“No Problem”)
- 1 (“Minor Problem”)
- 2 (“Moderate Problem”)
- 3 (“Major Problem”)
- 4 (“Don’t Know/Not Applicable”)

The imputation method used in the derivation of time to alleviation of influenza signs and symptoms is described below. No further imputation methods will be used.

In all time to event analyses, patients who withdraw prior to event of interest will be censored at the last observation timepoint.

If the number of patients in the ITTi set is small, then listings may be provided.

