### **Duration of Fever**

Duration of fever will be summarized using descriptive statistics, as well as Kaplan-Meier plots. It is defined as the time to return to afebrile state (tympanic temperature  $\leq 37.2^{\circ}\text{C}$ ) and remaining so for at least 21.5 hours.

Patients who do not return to afebrile state will be censored at the last observation time point.

Patients who are afebrile at baseline (tympanic temperature  $\leq 37.2^{\circ}\text{C}$ ) or whose body temperature is not collected will be excluded from the analysis.

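### TTAS is timed from dosing, but infants who already meet every criterion at the first post-dose assessment are left out, so qualifying early alleviations are deleted; duration of fever may share the problem.

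*SAP*

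**What the plan says.** **TTAS (SAP 4.3.1).** The endpoint is "the length of time taken from the start of treatment to the point at which all of the following criteria are met", sustained for 21.5 hours. The criteria are cough and nasal scores of 0 or 1, a yes to the normal-activity question, and a tympanic temperature of 37.2°C or below. Infants who satisfy all of them "simultaneously at baseline will be excluded from the analysis". On which reading that is, the SAP says: "Baseline is defined as the first CARIFS assessment on Day 1 after the start of treatment". Without a Day 1 post-dose entry, patients "will have their baseline CARIFS assessment set to missing". The schedule of activities (Protocol Appendix 1, footnote g; repeated in SAP Appendix 2) confirms that the first CARIFS comes after dosing.

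Two sensitivity analyses are planned. In the first, "A sensitivity analysis will be conducted that considers all assessments in the calculation of the TTAS", with a score of 4 not breaking alleviation. In the second, "a sensitivity analysis will be conducted in which the following criterion will be removed from the calculation of the TTAS"; the criterion concerned is the activity question.

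**Duration of fever (SAP 4.3.1).** "It is defined as the time to return to afebrile state", again sustained for 21.5 hours, with no starting point given. Infants afebrile at baseline, or with no temperature collected, are excluded. The paragraph does not say which reading is baseline. SAP 4.2.1.5 defines a baseline for diary temperature, namely the first Day 1 reading after treatment, but the fever paragraph does not refer to it.

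**What exists before dosing.** Protocol 4.5.4 lists tympanic temperature among the vital signs, and the schedule places vital signs at Visit 1 screening.

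**The concern.** An exclusion meant to remove patients with nothing left to alleviate should rest on their state before the clock starts. Here it rests on a reading taken after the clock has started, so an outcome helps to decide membership of the analysis. An infant who is alleviated by the first CARIFS and stays so for 21.5 hours meets the event definition and is still deleted.

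The exclusion also differs from the event in one respect: it needs a single qualifying reading, with no persistence. An infant who qualifies once, relapses and recovers days later is therefore deleted as well.

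TTAS is the key secondary endpoint, and Kaplan-Meier medians are the main time-to-event summaries for about 30 infants. In a single-arm study there is no comparator in which the same deletion could cancel.

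**Working it through.** **1. Who is removed.** The TTAS exclusion catches three kinds of infant:

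- (a) unalleviated at dosing, alleviated by the first reading, and sustained: a true early event, and its loss lengthens the median;
- (b) qualifying at the first reading only, then relapsing: a later event, and its loss shortens the median if that event lies above the median;
- (c) already meeting the criteria before dosing: reasonably excluded.

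Entry requires one respiratory symptom of any severity and no fever (Protocol 4.1.1), so (c) is plausible. Without a pre-dose CARIFS, (a) cannot be separated from (c).

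**2. Whether a planned analysis brings them back.** The first sensitivity analysis changes only how a score of 4 is handled. The second removes the activity question from the calculation and does not say whether the exclusion changes too; if it did, more infants would qualify for exclusion, not fewer. Neither restores (a) or (b).

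**3. Effect per infant, with no lag assumed.** The plan gives no figure to reproduce. If *a* infants are lost below the median and *b* above it, the reported median is the quantile q = 0.5 + (a − b)/(2n) of the full set. For size, assume S(t) = 2^−((t/m)^k), so that the new median is m·(−log2(1 − q))^(1/k). Inputs: n = 30; k = 1 to 2 (assumed); m = 44.6 h for alleviation and 21.4 h for fever, both from the Japanese paediatric study in Protocol 1.2.4. That study enrolled children from 6 months to under 12 years, and its alleviation endpoint had no activity question.

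- a − b = 1: q = 0.5 + 1/60 = 0.517. TTAS moves by +2.2 h (k = 1) or +1.1 h (k = 2); fever by +1.0 h or +0.5 h.
- a − b = −1: q = 0.483. TTAS moves by −2.1 h or −1.1 h.
- a = b: no change.

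**4. How many of kind (a).** The documents give no time from dose to first reading, so the lag L is an assumption. The fraction lost is f = 1 − 2^−((L/m)^k), and the median of the rest is (m^k + L^k)^(1/k). For TTAS, with every infant unalleviated at dosing and only kind (a) lost:

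| L | Lost of 30, k = 2 to k = 1 | Shift in median |
|---|---|---|
| 2 h | 0.0 to 0.9 | 0.0 to 2.0 h |
| 4 h | 0.2 to 1.8 | 0.2 to 4.0 h |
| 8 h | 0.7 to 3.5 | 0.7 to 8.0 h |

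The diary periods in SAP Table 4 bound L loosely. A 05.00 dose with an entry at the end of the evening period gives L = 13.98 h, 2.0 to 5.9 infants and 2.1 to 14.0 h. These shifts are upward only because kind (b) is left out.

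**5. Against sampling error.** The approximate 95% half-width of the median, uncensored, is 1.96·m/(k·ln 2·√30). For TTAS this is 23.0 h at k = 1 and 11.5 h at k = 2; for fever, 11.0 h and 5.5 h. Every TTAS shift above is smaller than the half-width for the same k.

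**6. Fever.** If the SAP 4.2.1.5 baseline and a dosing origin apply, the structure is that of step 1. With all infants febrile at dosing and L = 4 h, f is 2.4% (k = 2) to 12.2% (k = 1), or 0.7 to 3.6 of 30, and the shift is 0.4 to 4.0 h. Infants never febrile would be indistinguishable from infants whose fever fell after dosing. Here, unlike TTAS, a scheduled pre-dose reading could separate them.

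**The case against.** The main TTAS rule can be defended. The first post-dose CARIFS is the earliest that exists, and infants who were mild before dosing should not be credited as alleviations on treatment. That stands, and it is why the main analysis should stay as it is. Nor is a post-dose baseline an error in itself: the SAP uses one harmlessly for laboratory data. The difficulty is letting it decide entry to an endpoint timed from dosing. Overall duration of symptoms, by contrast, keeps every patient whatever the baseline.

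The size is unknown. Lag, hazard shape and medians are all assumed or borrowed, so the hours above are illustrative and are not evidence of bias. This also stands.

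Four stronger readings are tempting, and the documents do not support them:

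- *The fever baseline is undefined.* SAP 4.2.1.5 defines one for the same diary variable. What is missing is a statement that it applies, and a time origin.
- *The fever clock might start at the baseline reading.* Nothing in the SAP starts an endpoint there. Where it states an origin (TTAS and both viral-shedding times), the origin is the initiation of treatment.
- *The same recovery is excluded if first recorded on Day 1 but counted if first recorded on Day 2.* The SAP does foresee late devices ("In the case where the device was activated after Day 1") and sets a missing baseline to missing, but it is silent on whether such infants enter the analysis. This is possible, not established.
- *The TTAS median is overstated.* Losing infants of kind (b) can pull the other way, so the sign is not known in advance.

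**Conclusion.** The TTAS point holds on the SAP's explicit text: a post-treatment reading decides entry to an endpoint timed from dosing, qualifying early events are deleted, and no planned analysis restores them. For duration of fever the point is conditional. It arises if the 4.2.1.5 baseline and a start-of-treatment origin apply, which is the natural reading but is not stated.

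The point is minor. The likely number of infants is small if the first entry follows dosing by a few hours, the net direction is unknown, and the illustrative shifts lie within sampling error at n = 30. No hypothesis test or decision rule depends on these medians. It is worth acting on because the change is cheap and uses data already scheduled.

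**What to change.** 1. **TTAS.** Keep the main analysis. Add a sensitivity analysis that retains all infants in the influenza-infected (ITTi) set and counts alleviation at the first post-dose assessment, if sustained for 21.5 hours, as an event at that time.
2. **Duration of fever.** State the start of treatment as the origin. Define entry by the last pre-dose tympanic temperature, using the first Day 1 post-dose reading only where that is missing; SAP 4.3.2 already uses this pattern for virology. Count a sustained afebrile state beginning at the first diary reading as an event at that reading. Keep entry by the 4.2.1.5 baseline as a sensitivity analysis.
3. **Reporting.** Give the number excluded under each rule and the distribution of time from dose to first reading.

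The cost is SAP wording and programming, with no new data. There are three drawbacks. The pre-dose temperature is taken in clinic and later ones at home, although both are tympanic. An antipyretic given before dosing can mask fever at entry; the fever sensitivity analysis, which uses a post-dose home reading, shows whether the choice of entry reading matters. The all-retained TTAS analysis counts infants already mild before dosing as early events, so it belongs beside the main analysis and does not replace it.

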#### **4.2.1.5 Body Temperature**

Body temperature is collected in the patient diary 4 times daily for Day 1–3, twice daily for Day 4–9 and once daily thereafter. Summary statistics of observation and the change from baseline in body temperature will be presented for each recorded time point.

Baseline is defined as the first recorded assessment on Day 1 after treatment. Patients who do not have body temperature recorded on Day 1 after the start of treatment will have their baseline body temperature set to missing.

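### The main analyses of TTAS and duration of symptoms discard diary entries that already record illness, so alleviation can be declared across them

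*SAP*

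**What the plan says.** SAP Section 4.3.1, under Time to Alleviation of Influenza Signs and Symptoms, defines TTAS as the time from the start of treatment until "all of the following criteria are met and remain so for at least 21.5 hours". The criteria are cough and nasal items (14 and 15) scored 0 or 1, a yes to the normal-activity question, and tympanic temperature of 37.2 °C or less.

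Two rules then remove entries from the main analysis.

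- If item 14 or 15 is scored 4, "the assessment will not be included in the calculation of the alleviation of symptoms because the assessment was unobservable".
- The main analysis uses "only complete assessments (i.e., assessments that have responses for items 14 and 15 of the CARIFS questionnaire, the normal daily activity question and temperature", so an entry lacking any one of these four responses is also removed.

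The Duration of Symptoms text has the same structure. An entry is removed for a 4 on any item except 10, 11 and 12, or if any of the 18 items lacks a response.

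Each endpoint has a sensitivity analysis that considers all assessments. The TTAS one is described as an analysis "where a score of 4 for items 14 or 15 does not break the incidence of alleviation". This is the only kind of wording on whether anything breaks a run, and it applies to the sensitivity analyses alone. The text after Table 4 says "The imputation method used in the derivation of time to alleviation of influenza signs and symptoms is described below", but what follows for TTAS is exclusion, with no rule for gaps.

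**The concern.** The TTAS definition requires every criterion to hold throughout 21.5 hours. One observed failure at a time point therefore settles that the infant is not alleviated then, whatever else is unknown. An entry with cough scored 3 and nasal symptoms scored 4 is not unobservable in the sense that matters, because its status is known. The main analysis nevertheless sets it aside.

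The effect depends on a convention that the SAP leaves unstated. If the entry is skipped, the passing entries on either side can join into a qualifying run and the result contradicts the endpoint's definition. If it breaks the run, the recorded illness is respected, but an entry that passes on everything observed and has a single 4 is treated as illness. Two programmers could follow the text faithfully and report different times for the same infant. TTAS is the key secondary efficacy endpoint in SAP Table 1.

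**Working it through.** The plan gives no figure to reproduce, so the check applies the rules to example diaries.

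**How many entries a run needs.** SAP Table 4 sets morning as 05.00–10.59 and evening as 15.00–18.59. CARIFS is due morning and evening on Days 1 to 9 (SAP Appendix 2, footnote g).

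- Longest gap, morning to same evening: 18:59 − 05:00 = 13 h 59 min.
- Longest gap, evening to next morning: 24:00 − 15:00 + 10:59 = 19 h 59 min.

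Both are below 21.5 h, so on Days 1 to 9 a qualifying run spans at least three scheduled entries. A dropped middle entry brings the unstated gap rule into play.

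**Example diaries (clock times assumed).** Dose at 10:00 on Day 1; CARIFS at 08:00 and 17:00. Entries then fall at 7, 22, 31, 46, 55 and 70 h after dosing. The 7 h entry fails (cough 2, activity no, 38.0 °C), so the infant is not excluded as alleviated at baseline. All later entries pass except as stated.

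| Case | Changed entry | Skipped | Breaks run | Any observed failure counts; other gaps do not break |
|---|---|---|---|---|
| A | 31 h: cough 3, nasal 4 | 22 h | 46 h | 46 h |
| C | 22 h: nasal 4, rest passing | 31 h | 31 h | 31 h |
| D | 31 h: nasal 4, rest passing | 22 h | 46 h | 22 h |

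- A, skipped: the run goes from 22 to 46 h; 46 − 22 = 24 ≥ 21.5, so TTAS is 22 h. If the illness counts, the run restarts at 46 h; 70 − 46 = 24 ≥ 21.5, so TTAS is 46 h. The same results follow if the 31 h entry has cough 3 and activity no with temperature missing.
- C: the run starts at 31 h; 46 − 31 = 15 is too short, and 55 − 31 = 24 qualifies. TTAS is 31 h, against 22 h if the nasal item was truly 0 or 1.
- D: same arithmetic as A, but here skipping is the sensible result.

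The unstated convention moves TTAS by 46 − 22 = 24 h in A and in D, and neither choice handles both. Duration of symptoms behaves likewise: an evening with cough 3 and item 18 scored 4 gives 22 h if skipped and 46 h if the illness counts.

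**How often entries might be dropped.** The documents give no rate of 4s. Assume each item has chance q of a 4, independently. The share of entries dropped for a 4 is 1 − (1 − q)^k, with k = 2 for TTAS and k = 18 − 3 = 15 for duration of symptoms.

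| Assumed q | TTAS | Duration of symptoms |
|---|---|---|
| 1% | 2% | 14% |
| 5% | 10% | 54% |
| 10% | 19% | 79% |

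These are shares of entries dropped for any 4. The share that also records illness is smaller and cannot be derived.

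**The case against.** The strongest reply is that the plan already holds the answer. Each all-assessments sensitivity analysis counts an entry with cough 3 and nasal 4 as illness, and gives 46 h in case A. The SAP tabulates missing CARIFS and scores of 4, so a reader can see whether the problem arises, and Protocol Section 4.5.6 asks for the questionnaire to be completed in full. The endpoints are descriptive, in about 30 infants, with no hypothesis test. The proposed rule also works in one direction against the skipping reading: it keeps partial entries that show illness but does not credit partial entries that pass.

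Much of this stands, and it limits the importance of the point. It does not remove it. The sensitivity analyses leave the main estimate uncorrected, and they give no rule for blank responses. The asymmetry comes from the definition: one failure disproves alleviation, while proof needs every component.

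A reader might go further and infer that TTAS will precede the same infant's duration of fever. The SAP says "Body temperature is collected in the patient diary 4 times daily" on Days 1 to 3, while CARIFS is due twice daily, so 6 of the 12 scheduled temperatures have no CARIFS entry. With a reading of 38.5 °C at bedtime on Day 2, TTAS could be 22 h and duration of fever 46 h. That requires TTAS to ignore the bedtime reading and duration of fever to use it. The SAP states neither, so the inconsistency is possible but not demonstrated.

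**Conclusion.** The point holds for the main analyses of both endpoints. The rule can give a time that contradicts the 21.5-hour definition, and stating a gap convention alone would not repair it. In the examples, one entry moves one infant's TTAS by 24 h. That rests on assumed clock times and constructed diaries, and it is not an estimate of the effect on the reported median. The primary safety analysis and the sample size are unaffected.

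Three stronger readings are not supported.

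- The main TTAS is not shown to be too short overall. Dropped passing entries delay it (case C), so the net bias is unknown.
- The temperature pairing is a matter for clarification, not a demonstrated contradiction.
- Censoring for duration of symptoms is not absent. The general text after Table 4 censors patients who withdraw before the event in all time-to-event analyses. Only infants who complete the study without an event lack explicit wording in that section.

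**What to change.** In the main analyses of both endpoints:

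- Count an entry as not alleviated if any observed component fails, whatever else is missing or scored 4.
- Count it as alleviated only if all required components are observed and pass, with items 10 to 12 handled as now.
- Treat the remaining entries as unobservable and state the gap rule. A workable one is that they do not break a run, but a run must start and end at fully observed passing entries.

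Keep the current rule, with its gap convention stated, and the planned all-assessments analyses as sensitivity analyses. The latter still matter for case C and for infants repeatedly scored 4 on one required item, who have no fully observed passing entry.

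As a clarification, state which diary temperatures pair with CARIFS for TTAS and which count for duration of fever, so that the two endpoints are consistent.

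The cost is a few SAP sentences and some derivation code, with no new data. Compared with skipping dropped entries, the change can only leave TTAS equal or make it later, and the delay in case C remains in the main analysis.
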